13.3. Primary Endpoint

At the end of data collection all subjects enrolled will be randomly assigned to the derivation set and the validation set at a ratio of 2 to 1. According to the outcome of the planned RD event rate monitoring, there could be the possibility to use the overall population as the derivation cohort. The validation sets will be performed using a bootstrapping method. A detailed description of the bootstrap method will be

Version 3.0, 29 Nov 2016

PRODIGY CIP

reported in the Statistical Analysis Plan (SAP). Bivariate odds ratios (ORs) and 95% confidence intervals (95% CIs) will be estimated. The possibility of collinearity between categorical variables will be also tested. The logistic regression model will be performed using a backward stepwise selection procedure in which the presence of event will be the dependent variable. Independent predictors will be entered into the model if a significant association, defined as $p \le 0.05$, will be identified from bivariate analysis and, to avoid over-fitted and unstable model the correlation coefficient between them should be less than 0.25.

The predictive risk score for RD will be calculated by multiplying each b coefficient (from the multivariate model by 10 and rounding to the nearest integer. The integers will then be added together to produce an overall RD risk score for each subject. The resulting continuous distribution of total risk scores across all subjects in the derivation set will be then stratified into 3 categories of points that grouped subjects according to the level of risk (low, medium and high risks). Model prediction performance will be assessed using calibration (the agreement between predicted and observed outcome) and discrimination (the ability to separate subjects with and without the outcome) and the R2 will be reported as an overall measure for discrimination and calibration. The Sensitivity and Specificity and the receiver-operating characteristic (ROC) curves will be used to visualize the overall accuracy of the model. The discriminatory performance of the model will be validated by comparing the ROC curve analysis in the derivation set with that in the validation set.

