7.10.1.1 Deriving the model

Note for Programmer: The analysis for the primary objective will be performed on a Dataset with one row per patient with RD episode as validated by CEC as the dependent variable (at least one RD) and baseline predictors as independent variables. Potential predictors will be reported on continuous scale or grouped into categories.

The logistic model will be used for bivariate e multivariate odds ratios (ORs) and 95% confidence intervals (95% CIs) will be estimated for each potential predictor. The following steps will be followed to derive the score for each predictor according to categories⁴:

- Determine categories for each risk factors (the most will be 0/1)
- Determine reference class for each risk factor (for dummy the reference category is 0)
- Calculate mid-values to represent categories
- Determine multiplier β
- Determine point score for each risk factor category

If **Data Split** approach:

- Repeat multivariate model on the validation set
- Calculate performance measures
- The "Optimism" is the difference between the performance measures from validation and derivation set

If **Bootstrapping** approach:

- 500 bootstrapped replications of the multivariate model

- Calculate performance measures bootstrapped
- The difference between the bootstrapped performance and the model performance will be averaged to obtain an estimation of the “optimism” of the model. The optimism will be used to validate the model.

Table 25 - RD Risk Score Derivation identified by logistic – MFAS

Predictors	Bivariate analysis OR (95% CI) (N=XXXX)	Multivariate analysis OR (95% CI) (N=XXXX)	Coefficient	Adjusted Coefficient	Risk score point
Char#1	x.xx (x.xx- x.xx)	x.xx (x.xx- x.xx)	x.xxx	x.xx (x.xx- x.xx)	xx
Char#2	x.xx (x.xx- x.xx)	x.xx (x.xx- x.xx)	x.xxx	x.xx (x.xx- x.xx)	xx
...					
Char#N	x.xx (x.xx- x.xx)	x.xx (x.xx- x.xx)	x.xxx	x.xx (x.xx- x.xx)	xx

The collinearity between categorical variables will be also tested by means the Cramer V test for nominal variables and Kendal’s tau-b for ordinal variables. The multivariate logistic regression model will be performed using a stepwise selection procedure in which the presence of event will be the dependent variable. Independent predictors will be entered in to the model if a significant association, defined as $p \leq 0.05$, will be identified from bivariate analysis and, to avoid over-fitted and unstable model the correlation coefficient between them should be less than 0.25.

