The predictive risk score for RD, based on the best model selected from analysis above, will be calculated by multiplying each β coefficient taken from the final multivariate model by 10 and rounding to the nearest integer. The integers will then be added together to produce an overall RD risk score for each patient. The resulting continuous distribution of total risk scores across all patients in the derivation set will be then stratified into categories of points (depending on the total sample the quintiles or tertiles or optimal cutoff points) that grouped patients according to the level of risk.

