7.10.1.2 Validating model on validation cohort

Model prediction performance will be assessed as for the derivation cohort using calibration (the agreement between predicted and observed outcome) and discrimination (the ability to separate patients with and without the outcome) and the R^2 will be reported as an overall measure for discrimination and calibration. The Sensitivity, Specificity, Positive Predictive Value (PPV), Negative Predictive Value (NPV) and the Receiver Operating Characteristic (ROC) curves will be used to visualize the overall accuracy of the model (see section 9.1 for detail on aspect to be checked for model validity).

Table 26 - Sensitivity, specificity, PPV and NPV of the Risk Score to predict high risk subjects – Validation Cohort - FAS

Accuracy Measure	Optimal Cut-off %(IC)
Sensitivity	X% (Y%-Y%)
Specificity	X% (Y%-Y%)
PPV	X% (Y%-Y%)
NPV	X% (Y%-Y%)
...	...

Figure 3 – Receiver Operating Characteristics curve on Validation Cohort-FAS

Figure 4 – Agreement between observed frequency and predicted probability on Validation Cohort- FAS

The discriminatory performance of the model will be validated by comparing the receiver-operating characteristic (ROC) curve analysis in the derivation set with that in the validation set.

Figure 5 – Comparison between ROC curves on Derivation and Validation Cohorts-FAS

Figure 6 – RD rate according to the Risk Score in Derivation and Validation Cohorts-FAS

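### The risk-score cut-off has no pre-set rule or stated source, so the sensitivity, specificity, PPV and NPV reported at it may be optimistic

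*SAP*

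**What the plan says.** Protocol 13.3 has the total score "stratified into 3 categories of points that grouped subjects according to the level of risk", named low, medium and high. It does not say how the boundaries are found.

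SAP 7.10.1.1 has "The resulting continuous distribution of total risk scores across all patients in the derivation set will be then stratified into categories of points", and gives the method as "depending on the total sample the quintiles or tertiles or optimal cutoff points". No condition decides which option applies, optimal is not defined, and the number of categories under that option is not stated.

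Table 26 in SAP 7.10.1.2 is titled "Sensitivity, specificity, PPV and NPV of the Risk Score to predict high risk subjects – Validation Cohort - FAS". It has one results column, at an optimal cut-off, and does not name the data set that supplied it. SAP 9.1 says the clinical-usefulness measures need a threshold but gives neither a value nor a rule.

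If the cohort is split, SAP 7.10.1.1 instructs: "Repeat multivariate model on the validation set". If the bootstrap is used, the same section has performance measures bootstrapped and their average difference from the model's performance taken as the optimism. SAP 9.2 describes what is run in each of the 500 replications, namely the univariate and multivariate models, and works out optimism for R² only. SAP 7.2 leaves the choice between split and bootstrap to the end of data collection.

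**The concern.** The accuracy figures at the cut-off are the ones a ward would use to decide which patients to monitor. If a cut-off is picked because it gives the best sensitivity and specificity in some group of patients, those figures look better in that group than they would in new patients. Protocol 6.2 gives exactly this reason for having a validation step.

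The plan leaves two ways for this to happen:

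- **Data split.** Nothing says that the Table 26 cut-off is the derivation cut-off applied unchanged. The instruction to repeat the model on the validation set reads as a refit. A refit changes the coefficients and so the integer points, and a derivation cut-off would then no longer sit on the same scale. A programmer could reasonably search for a new one.
- **Bootstrap.** There is no second cohort. An optimal cut-off is chosen and first evaluated on the same patients, and no text says that the search is repeated in each replicate.

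There is a further gap. Three categories have two boundaries (quintiles have four), while Table 26 needs one. No rule says which boundary defines high risk.

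**Working it through.** **1. Sizes, from protocol 13.1 and SAP 6.**
- Derivation: 12 variables × 10 events / 0.12 = 1000.
- Total before attrition: 1000 / (2/3) = 1500, so validation = 500.
- Attrition: 1500 × 1.1 = 1650, the plan's figure (1500 / 0.9 would give 1667).
- Validation cohort: 500 × 0.12 = 60 with RD and 440 without.
- Bootstrap route, all 1500: 180 with RD and 1320 without.

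**2. Assumptions, because the documents give no values.** The score is normal in both groups with equal variance. The ROC area is 0.60 to 0.80, with separation d = √2 × Φ⁻¹(area). Optimal means the cut-off that maximises sensitivity + specificity (Youden). Excess = figure observed at the chosen cut-off minus the true figure at that same cut-off.

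**3. Cut-off chosen on 500 validation patients, against a cut-off chosen on 1000 derivation patients and applied unchanged.** Integer score with an SD of 6 points, 12% prevalence, 4000 runs per row.

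| ROC area | Sensitivity observed / true (%) | Specificity observed / true (%) | Excess in sum (points) | Excess if carried over (points) |
|---|---|---|---|---|
| 0.60 | 60.1 / 55.0 | 58.4 / 57.8 | 5.7 | −0.02 |
| 0.65 | 64.0 / 59.3 | 61.2 / 60.6 | 5.4 | 0.11 |
| 0.70 | 67.0 / 62.8 | 65.1 / 64.6 | 4.7 | 0.07 |
| 0.75 | 70.6 / 66.9 | 68.9 / 68.4 | 4.3 | 0.07 |
| 0.80 | 74.4 / 71.1 | 72.8 / 72.4 | 3.7 | −0.05 |

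With the cut-off chosen and evaluated on 1500 patients, the excess in the sum is 2.8, 2.5, 2.1, 1.9 and 1.7 points for the same five areas.

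**4. Effect of score granularity.** The score is a sum of rounded points from mostly 0/1 factors, so it may take few distinct values. Excess in sensitivity + specificity (points), 3000 runs per cell:

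| Score step | 60/440, area 0.60 / 0.70 / 0.80 | 180/1320, area 0.60 / 0.70 / 0.80 |
|---|---|---|
| Continuous | 7.2 / 6.3 / 5.5 | 3.9 / 3.1 / 2.7 |
| 0.25 SD | 5.4 / 4.3 / 3.5 | 2.6 / 1.9 / 1.6 |
| 0.5 SD | 4.3 / 3.2 / 2.3 | 2.0 / 1.3 / 0.9 |
| 1 SD | 3.1 / 1.3 / 0.3 | 1.3 / 0.1 / 0.0 |
| 2 SD | 2.3 / 0.6 / 0.1 | 1.1 / 0.0 / 0.1 |

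Most of the excess is in sensitivity, because few patients have events. For the continuous score at area 0.70 with 60/440, 5.7 of the 6.3 points are sensitivity.

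**5. Predictive values at area 0.70**, from the mean figures in step 3 and 12% prevalence:
- PPV observed: 0.12 × 0.670 / (0.12 × 0.670 + 0.88 × 0.349) = 20.7%. PPV true: 0.12 × 0.628 / (0.12 × 0.628 + 0.88 × 0.354) = 19.5%.
- NPV observed: 0.88 × 0.651 / (0.88 × 0.651 + 0.12 × 0.330) = 93.5%. NPV true: 0.88 × 0.646 / (0.88 × 0.646 + 0.12 × 0.372) = 92.7%.

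**The case against.** The strongest reply is that the SAP, read in order, already does the right thing. Section 7.10.1.1 forms the categories, including any optimal cut-off, on scores in the derivation set, and Table 26 then uses the same term. On that reading the cut-off is carried over and step 3 shows essentially no bias. This reply stands against the tempting claim that Table 26 will be optimistic: no text says its cut-off is chosen on the validation cohort. It does not close the gap. The sentence covers forming categories, does not say that Table 26 uses those boundaries, and sits beside an instruction that reads as a refit.

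A reader might also infer that the bootstrap corrects R² alone. The documents do not support that either, since SAP 7.10.1.1 speaks of performance measures in general and SAP 9.1 lists sensitivity and specificity among them. What stands is that the two bootstrap descriptions differ and neither mentions repeating the cut-off search.

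Three more points are fair and stand:
- Tertiles and quintiles do not use the outcome, so only the optimal option can cause this bias.
- Tertiles would keep the protocol's three categories, and the SAP's condition on the total sample may refer to sample size only. Even so, no size thresholds are given.
- The ROC comparison, calibration and Brier score need no cut-off, so it would be wrong to say that the validation as a whole is defeated.

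**Conclusion.** The point holds as a conditional one. The rule for the cut-off is open, the SAP allows a departure from the protocol's three categories, and the source of the Table 26 cut-off is not stated. Accuracy reported at that cut-off may therefore be optimistic. On the bootstrap route, an optimal cut-off would be chosen and first evaluated on the same patients, and correction of accuracy at the cut-off is not assured.

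If an outcome-based cut-off is chosen on the patients who are then used to report accuracy, sensitivity plus specificity is overstated by about 0 to 7 points with 60/440 patients. With 180/1320 the range is about 0 to 4 points before model overfitting. The excess is mostly in sensitivity and is smallest when the score has few distinct values. These ranges rest on assumed ROC areas of 0.60 to 0.80, the Youden index, a normal score and the score steps shown. If score and cut-off are carried over unchanged from derivation, the bias is essentially nil.

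**What to change.** - Keep the protocol's three categories. State in the SAP how the two boundaries are found, which one defines high risk in Table 26, and what criterion optimal means if that option is kept.
- **Data split:** derive the integer score and the cut-offs in the derivation set and apply both unchanged to the validation cohort in Table 26. If the model is also refitted there, report the refit separately and do not use it for Table 26.
- **Bootstrap:** in every replicate, repeat model selection, point assignment and the cut-off search. Compare accuracy at that cut-off in the replicate with its accuracy in the original sample, and report optimism-corrected sensitivity, specificity, PPV and NPV. Align SAP 9.2 with the bootstrap steps in 7.10.1.1.

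The cost is SAP wording, a little more programming and slightly less favourable reported accuracy. No new data are needed.

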7.10.1.2 Validating model on validation cohort

Model prediction performance will be assessed as for the derivation cohort using calibration (the agreement between predicted and observed outcome) and discrimination (the ability to separate patients with and without the outcome) and the R^2 will be reported as an overall measure for discrimination and calibration. The Sensitivity, Specificity, Positive Predictive Value (PPV), Negative Predictive Value (NPV) and the Receiver Operating Characteristic (ROC) curves will be used to visualize the overall accuracy of the model (see section 9.1 for detail on aspect to be checked for model validity).

Table 26 - Sensitivity, specificity, PPV and NPV of the Risk Score to predict high risk subjects – Validation Cohort - FAS

Accuracy Measure	Optimal Cut-off %(IC)
Sensitivity	X% (Y%-Y%)
Specificity	X% (Y%-Y%)
PPV	X% (Y%-Y%)
NPV	X% (Y%-Y%)
...	...

Figure 3 – Receiver Operating Characteristics curve on Validation Cohort-FAS

Figure 4 – Agreement between observed frequency and predicted probability on Validation Cohort- FAS

The discriminatory performance of the model will be validated by comparing the receiver-operating characteristic (ROC) curve analysis in the derivation set with that in the validation set.

Figure 5 – Comparison between ROC curves on Derivation and Validation Cohorts-FAS

Figure 6 – RD rate according to the Risk Score in Derivation and Validation Cohorts-FAS

7.10.2 Secondary endpoints

For secondary endpoints the MFAS population will be used for analysis.

7.10.2.1 Secondary endpoint#1

The secondary objective#1 will be evaluated comparing subjects that will develop RD versus patients that will not develop RD in terms of:

- Incidence of AE and actions taken.
- Healthcare resource utilization (including hospital length of stay, 30 days readmission rate and primary diagnosis upon readmission).
- Subject mortality at 30 days.

This secondary objective will be explained in the Health Economic Analysis Plan (HEAP).

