Ethical Committee / Institutional Review Board	EC / IRB	Any board, committee, or other group formally designated by an institution to review, to approve the initiation of, and to conduct periodic review of, biomedical research involving human subjects. The primary purpose of such review is to assure the protection of the rights and welfare of the human subjects.
End Tidal CO2	etCO ₂	The numeric partial pressure of the maximum value of carbon dioxide in the exhaled breath over the last 20 seconds. The etCO ₂ numeric value is updated once a second.
Emergency Room	ER	Medical treatment facility specializing in emergency medicine, the acute care of patients who present

Version 3.0, 29 Nov 2016

Term	Abbreviation	Definition
		without prior appointment; either by their own means or by that of an ambulance.
Fractional inspired carbon dioxide	FiCO ₂	The numeric partial pressure of carbon dioxide present during inhalation.
Intensive Care Unit	ICU	Acute care with 24 hour coverage. Patients may be directly transferred direct from the OR to the ICU or via the PACU.
Integrated Pulmonary Index™	IPI	The Integrated Pulmonary Index (IPI) is a composite index of $etCO_2$, SpO_2 , RR and PR that is intended to indicate changes in physiological status as indicated by the monitored variables and cleared by FDA (K082268) in 2009.
Pulse Rate	PR	Pulsatile cycle in beats per minute via pulse oximeter technology.
Pulse Oximetry	SpO₂	Depends on pulsatile blood flow and measures only the oxygemoglobin in arterial blood as it leaves the heart.
Remote Data Capture	RDC	An interface that allows site users at sites to enter data directly into the study database via a web interface. RDC is an example of Electronic Data Capture method or EDC.
Respiratory Compromise	RC	Respiratory compromise consists of respiratory insufficiency, compromise, distress, arrest, and failure. Respiratory Compromise is a state in which there is a high likelihood of decompensation into respiratory insufficiency, respiratory failure or death, but in which specific interventions (enhanced monitoring and/or therapies) might prevent or mitigate decompensation.
Respiratory Depression	RD	Respiratory depression is a clinical diagnosis made after reviewing monitoring data in conjunction with the clinical data and consistent with accepted pathophysiologic mechanisms.
Respiratory Opioid- Related Adverse Events (ORADE)	rORADE	An episode of respiratory compromise that is related to opioid analgesia therapy.

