5.2. Endpoints

5.2.1. Primary Endpoint

Respiratory depression is a clinical diagnosis made after reviewing monitoring data in conjunction with the clinical data and consistent with accepted pathophysiologic mechanisms.

Version 3.0, 29 Nov 2016

PRODIGY CIP

The primary endpoint used to derive the score will be the incidence of RD episodes captured by continuous capnography and pulse oximetry measurements recorded on the Capnostream device memory data in conjunction with the clinical data as reported by the investigator.

RD determination will be validated by an independent Clinical Event Committee (CEC). The CEC will use both clinical data and monitor parameters specificed below as a guideline; if determination of an RD episode is clinically appropriate but outside of the guidelines a rationale will be provided.

Data suggestive of an RD episodes include any of the following:

- etCO₂ \leq 15 or \geq 60 mmHg for \geq 3 minutes.
- or
 - RR ≤ 5 breaths for ≥ 3 minutes.
- or
 - SpO₂ \leq 85% for \geq 3 minutes.
- or
 - Apnea episode lasting > 30 seconds.
- or
- Any respiratory Opioid-Related Adverse Event (rORADE).

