10.3. Risk-Benefit Rationale

Medtronic believes that the potential risks associated with the conduct of this study are minimal using non-significant risk, non-invasive study devices for the following reasons:

- All the devices used in the study are commercially available and used within their intended use.
- Standard of care will be followed by the sites for the administration of opioid therapy. Additional surveillance will be provided for close monitoring and recording of the subjects clinical status.

11. Adverse Event Assessments

In this study the following Adverse Events (AE) will be collected:

- All AEs with an underlying respiratory cause
- All adverse device effects (ADE)
- All Serious Adverse Events (SAE) (including sepsis events or related to opioid therapy)

RD episodes will not be considered Adverse Events if the subject is asymptomatic and no actions are taken.

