7.10.1 Primary endpoint

The primary endpoint that will be used to derive and validate the risk score assessment is the RD episode, defined as a clinical diagnosis made after reviewing monitoring data in conjunction with the clinical data and consistent with accepted pathophysiologic mechanisms. The primary endpoint used to derive the score will be the occurrence of RD episodes captured by continuous capnography and pulse oximetry measurements recorded on the Capnostream device memory data in conjunction with the clinical data as reported by the Investigators. RD determination will be validated by an independent Clinical Event Committee (CEC). The CEC will use both clinical data and monitor parameters specified below as a guideline; if determination of an RD episode is clinically appropriate but outside of the guidelines a rationale will be provided. Data suggestive of an RD episode include any of the following:

RR ≤ 5 breaths for ≥ 3 minutes
SpO2 ≤ 85% for ≥ 3 minutes

etCO ₂ ≤ 15 or ≥ 60 mmHg for ≥ 3 minutes
Apnea episode lasting > 30 seconds
Any respiratory Opioid-Related Adverse Event (rORADE)

The assessment of RD episodes will be made by the analysis of the Capnostream and clinical data for each patient. For each patient all potential RD episodes will be derived using the Detection Tool (see section 9.3) and will be submitted to the CEC according to a Priority List (see section 9.4) in order to adjudicate the potential RD episodes starting from RD episodes most likely to be RD. The CEC adjudication will stop the adjudication at the first RD occurring per patient (all details on CEC process are reported in the CEC Charter version 3.0).

All potential RD episodes in the study will be always rated by 3 coders (see detail in the Clinical Events Committee Charter Template, Version 3.0).

Patients of the MFAS will be randomly assigned (2:1) into respectively the derivation and the validation cohort. In case of low enrollment rate or low episode rate or according the outcome of a preliminary assessment of the events per variable or unbalanced enrollment per site/country the MFAS could not be randomized but used for model building and the bootstrap method, deriving 500 computer-generated samples by random selection with replacement for model validation³ (see section 9.2 for details).

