9.4 Priority List

The CEC will stop the adjudications at the first RD for each patient, while they will adjudicate all Clinical Events. In order to optimize CEC time the following priority list will be used to prioritize some Episode-File to be review first:

Priority 1: all clinical events with/without any episode from device data. In case multiple Clinical events per patient the CEC will review them using the time of occurrence, from first clinical event to the last.

Priority 2: Multiple episodes involving at least two parameters among SpO₂, EtCO₂, RR and Apnea. In case of multiple Episode-Files with this priority the CEC will review first the Episode-Files with the higher number of Episodes within the Episode-Files.

Priority 3: Multiple Episodes of the same parameter. In case of multiple Episode-Files with this priority the CEC will review using this order: SpO₂, EtCO₂, RR and Apnea

Priority 4: Any overnight Episodes of the same parameter. In case of multiple Episode-Files with this priority the CEC will review using this order: SpO₂, EtCO₂, RR and Apnea

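### SAP 7.10.2.1 compares AE incidence and actions between RD and no-RD subjects without removing the AEs that are themselves the confirmed RD, so part of the excess is built in

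*SAP*

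**What the plan says.** **The comparison.** SAP 7.10.2.1 evaluates secondary endpoint 1 by "comparing subjects that will develop RD versus patients that will not develop RD in terms of" three things, the first being "Incidence of AE and actions taken". The others are healthcare resource utilization and 30-day mortality. The section leaves the details to a Health Economic Analysis Plan (HEAP), which is not among the documents. Protocol 13.4 plans a formal comparison of event rates between groups by a mixed Poisson or negative binomial model.

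**How a subject becomes RD.** Protocol 5.2.1 and SAP 7.10.1 list four device criteria and then "Any respiratory Opioid-Related Adverse Event (rORADE"). The Protocol glossary defines an rORADE as "An episode of respiratory compromise that is related to opioid analgesia therapy". The list serves as a guideline, and the CEC validates each determination. Under SAP 9.4 the first items the CEC reviews are "all clinical events with/without any episode from device data".

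**When an RD episode is an AE.** Protocol Section 11 states: "RD episodes will not be considered Adverse Events if the subject is asymptomatic and no actions are taken". Appendix A has a similar sentence, but its condition concerns invasive actions only.

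**The concern.** One event can do two jobs. It can set the group label, and it can then be counted in the outcome compared between the groups. An rORADE in the monitoring period that the CEC accepts as RD does both. So does a device-detected episode confirmed as RD that was symptomatic or acted upon. A no-RD subject cannot contribute a CEC-confirmed RD event to the AE count. Unless such events are removed, the RD group shows more AEs and more actions even if RD has no further consequence.

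What is at stake is interpretation. A significant difference could be read as showing that RD leads to AEs and interventions, when some of it only restates how the groups were formed. The primary objective, the risk score, is not affected.

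**Working it through.** **1. The plan's own figures.** Neither document gives a sample size, power or effect size for secondary endpoint 1, so the main sample size is used only to set group sizes.
- Events and derivation cohort (Protocol 13.1.1): 10 × 12 = 120 events; 120 / 0.12 = 1000 subjects.
- Total (Protocol 13.1.2): 1000 / (2/3) = 1500; 1500 × 1.10 = 1650. This reproduces the plan.
- RD incidence (Protocol 13.1): under independence, 1 − (0.986 × 0.90 × 0.99) = 12.1%, against the stated 12%.
- With 1500 evaluable subjects, 0.12 × 1500 = 180 are RD and 1320 are no-RD.

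**2. Share of RD subjects whose RD is also an AE.** The documents do not give this share, f. For illustration, take the intervention rates of 0.3% to 3.4% in Protocol 4.1. Assume that they apply to all subjects and that every such subject falls in the RD group.
- Low: f = 0.003 / 0.12 = 2.5%.
- Middle (assumed 1% of all subjects): f = 0.01 / 0.12 = 8.3%.
- High: f = 0.034 / 0.12 = 28.3%.

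**3. Built-in excess.** Let p0 be the risk of any other AE, equal in both groups. The documents give no value for it. The RD group's AE risk is 1 − (1 − p0)(1 − f), so the excess over p0 is f(1 − p0).
- 12% RD, negligible p0: about 2.5 to 28 points.
- 12% RD, p0 = 20%: 0.025 × 0.80 = 2.0 to 0.283 × 0.80 = 22.7 points.
- 41% RD (the highest incidence quoted in Protocol 4.1), negligible p0: 0.003 / 0.41 = 0.7 to 0.034 / 0.41 = 8.3 points.

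**4. Chance of a significant result from overlap alone.** This used a chi-square test on subjects with at least one AE, two-sided 0.05, 180 against 1320 subjects, 200,000 simulations per cell. Each cell gives the RD-group risk, the risk ratio and the percentage of simulations with p < 0.05.

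| f | p0 = 2% | p0 = 5% | p0 = 10% | p0 = 20% |
|---|---|---|---|---|
| 2.5% | 4.5%; 2.2; 52% | 7.4%; 1.5; 29% | 12.3%; 1.2; 17% | 22.0%; 1.1; 10% |
| 8.3% | 10.2%; 5.1; over 99% | 12.9%; 2.6; 96% | 17.5%; 1.75; 82% | 26.7%; 1.3; 54% |
| 28.3% | 29.8%; 14.9; 100% | 31.9%; 6.4; 100% | 35.5%; 3.6; 100% | 42.7%; 2.1; 100% |

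**5. After the fix.** With the RD-defining AEs left out and p0 equal in both groups, the same test rejects in 4.7% to 4.9% of simulations for p0 from 2% to 20%, close to the nominal 5%.

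**The case against.** Several stronger readings are tempting, and the documents do not support them.

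- **That every rORADE makes its subject RD, so the no-RD group has none.** The criteria are a guideline and the CEC can decline to call an event RD. Protocol 13.2 counts clinical outcomes within the monitoring period, at most 48 hours, while Protocol 9.1 collects AEs until study exit. A later rORADE is an AE but need not change the group.
- **That the comparison is wholly circular.** Protocol Section 11 also collects all serious AEs, all adverse device effects and all respiratory AEs, opioid-related or not. Many of these do not define RD.
- **That resource use and mortality are affected in the same way.** Length of stay, readmission and death are not RD criteria.

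Two further objections have weight. Protocol 5.2.2 forms the groups by RD risk rather than by RD occurrence. If risk came from a score built on baseline predictors, this overlap would not arise. But the objective in Protocol 5.1.2 and SAP 7.10.2.1 both use RD occurrence, so the conflict has to be settled and does not answer the point. Second, the HEAP may already handle RD-defining events. That cannot be checked, and the endpoint as stated in the two documents carries no exclusion.

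It is also fair that the objective is to compare, with no causal claim, and that how often RD is symptomatic or acted upon is worth reporting. That is a description of the RD group, however, and needs no test against subjects who cannot have the event.

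The illustration is soft. The intervention rates come from post-surgical patients, while this cohort is mixed. The 12% was derived from three device criteria, one of which (respiratory rate ≤ 8) differs from the endpoint's threshold (≤ 5).

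**Conclusion.** The point holds in a limited form. For AEs and actions taken, part of the difference between RD and no-RD subjects is built in, because a CEC-confirmed RD event that is also an AE sets the group and is then counted in the outcome. The amount is f(1 − p0). It ranges from under 1 point to about 28 points across the assumptions shown, and overlap alone can be anything from a modest inflation of the false-positive rate to near-certain significance. The size rests on three things the documents do not give: the share of RD subjects with such an event, the background AE risk, and the RD incidence actually observed. The direction does not depend on them: with equal background risk, any such overlap raises the RD group's count. This is a cheap improvement to a secondary comparison, not a fault in the primary analysis.

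**What to change.** 1. In SAP 7.10.2.1 and the HEAP, exclude from the AE and actions comparison every AE, with its actions, that the CEC adjudicated as RD. Report those events descriptively in the RD group.
2. As a sensitivity analysis, count only AEs and actions after a landmark common to both groups, such as the end of monitoring.
3. Reconcile the group definition in Protocol 5.2.2 (RD risk) with SAP 7.10.2.1 (RD occurrence).
4. Reconcile Protocol Section 11 (any action) with Appendix A (invasive actions), since this decides which RD episodes count as AEs.

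Two alternatives look simpler but do not work well. Counting only AEs after the first adjudicated RD fails because SAP 9.4 has the CEC work in priority order and stop at the first RD it confirms, which need not be the earliest, and because no-RD subjects have no matching start time. Forming groups by device criteria alone leaves the overlap in place, because a symptomatic device-detected episode is still an AE, and it sets aside CEC adjudication.

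The cost is small. The CEC already adjudicates all clinical events (SAP 9.4), and AE date, time and actions are already collected (Protocol 11.2). The downside is fewer events in the comparison.
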